6.3.4. POINT OF ENROLLMENT

Patients that sign consent will be considered a study candidate; however, he/she will only be included into the study upon meeting the inclusion and exclusion criteria detailed in Section 6.3 and the criteria listed below.

Study candidates will be considered enrolled in the study when all the criteria below have been met:

- successfully implanted with a commercially approved LivaNova Perceval bioprosthetic aortic heart valve
- all inclusion and exclusion criteria were met, and
- an informed consent was obtained (including date and signature)

The date of the enrollment will be the later of either the date the Informed Consent was signed, or the date of the implant of the valve.

6.3.5. CRITERIA FOR SUBJECT TERMINATION

All enrolled subjects will be followed until the end of the study except upon premature discontinuation in the study. Participation of a subject in the study should be discontinued when:

- The exclusion from the study is required for the subject's safety,
- Relevant IRB and/or regulatory authority withdraw approval(s),
- The subject decides to withdraw from the study,
- The surgeon decides it is no longer in the subjects best medical interest to continue, or
- The subject is lost to follow up.

The subject may withdraw his/her consent or cooperation (i.e. the subject refuses to participate further in the study) at any time without jeopardizing the normal standard of care.

6.3.6. STUDY ENDPOINTS DEFINITIONS AND ASSESSMENTS

The primary endpoint will be evaluated with statistical hypothesis tests formally defined in Section 10.

Primary endpoint

The primary endpoint is the incidence of reduced leaflet motion identified through 4D volume-rendered CT imaging at minimum 1 month after the end of the anticoagulation or dual antiplatelet therapy (expected within 1 to 6 months post-implant, preferably 3 months), as assessed by an independent Core Lab. Enrolled subjects not receiving anticoagulation or antiplatelet therapy at discharge will be assessed via 4D volume-rendered CT imaging at a minimum of 30 days after hospital discharge.

• Secondary endpoints

The secondary endpoints are as follows:

- 1. Incidence of reduced leaflet motion (thrombus) with subanalysis in symptomatic and asymptomatic subjects, based on CT outcomes, and anticoagulation and dual antiplatelet treatment modalities, up to 1 year post-implant.
- 2. Incidence of reduced leaflet motion on 2nd 4D volume-rendered CT scan with contrast up to 1 year post-implant, in subjects in which reduced leaflet motion was previously detected.
- 3. Incidence and relationship of reduced leaflet motion to the device, procedure, or other causes up to 1 year post-implant.
- 4. Freedom from valve safety events (all-cause mortality, valve reintervention, myocardial infarction, structural valve deterioration, moderate or severe valve regurgitation, valve endocarditis, valve thrombosis, thromboembolic events, hemolysis and major bleeding) up to 1 year postimplant.
- 5. NYHA classification at 1 year post-implant.
- 6. Hemodynamic performance up to 1 year post-implant through TTE assessed by Echocardiographic Core Lab.

6.3.7. CORE LAB

CT Scan

The MedStar Health Research Institute, located at MedStar Washington Hospital Center, Washington D.C., USA will serve as the Core Lab for CT for this clinical study. [name] will serve as the Core Lab PI. All CT scans, and TEEs done in place of a CT scan, will be sent to the Core Lab for analysis.

Echocardiography

The MedStar Health Research Institute, located at MedStar Washington Hospital Center, Washington D.C., USA will serve as the Core Lab for echo for this clinical study. [name] will serve as the Core Lab principal PI. All echoes, except the pre-implant TTE and the implant TEE, will be sent to the Core Lab for analysis. If there is an echo performed with an unscheduled visit, it may be sent to the Core Lab for analysis.

Each postoperative TTE should include all the views and measurements specified in the echocardiographic protocol (Appendix 2). A copy of the examination will be recorded and provided to the Core Lab for analysis.

The Core Lab will conduct a full analysis of the acquisitions and perform the required analysis. The Core Lab will discuss any discrepancies or data quality problems through the Sponsor or with the clinical site as necessary.

7. STUDY PROCEDURES

7.1. CLINICAL STUDY RELATED PROCEDURES

All qualified personnel performing selection, enrollment and/or follow-up procedures must be trained on applicable study material and procedures (e.g. protocol & appendices). The study devices should be used in accordance with the respective IFU.

Detailed instructions on the type of data to be collected and on the process of data to be followed for the completion of the eCRFs will be provided to the PIs during dedicated meetings or trainings.

Follow-up evaluations are expected to be conducted in an office, hospital or clinic setting and are to be performed by the PI or his/her designee. If the subject has moved, the site is to make every effort to obtain the data required for the study (including copies of source documents) from the subject's physician in the new location.

7.2. SCREENING & ENROLLMENT

Subjects shall be provided with relevant information about the study, including the potential risks and benefits, prior to enrollment. Only those subjects who voluntarily provided written informed consent to participate will be eligible for enrollment.

The following activities shall be completed BEFORE subjects will be considered enrolled in the study:

- Successfully implanted with a commercially approved LivaNova Perceval bioprosthetic aortic heart valve (according to the IFU)
- All inclusion and exclusion criteria were met
- An informed consent was obtained (including date and signature)

The following activities must be conducted AFTER inclusion of the subject in the study

- Obtain subject medical history and preoperative clinical conditions, including cardiac rhythm and NYHA class
- Operative details as per below

7.3. PRE-IMPLANT & IMPLANT DATA

Pre-implant information will be collected. These data will include:

- Subject characteristics and vitals (date of birth, sex, measured height and weight, blood pressure)
- Medical history (including previous cardiovascular surgery)
- Physical evaluation (including cardiac rhythm and NYHA functional classification)
- Medications
- Hemodynamic data

Information collected during the implant will be recorded on an eCRF and will include the following information:

- Implant details including surgical approach and valve information
- Surgical procedural data
- Valve lesion type, pathology, and etiology
- Concomitant procedures
- Hemodynamic data
- SAEs
- Subject outcome
- Cardiac rhythm
- Medications

7.4. Intraoperative TEE is a routine part of the standard of care in management of valve subjects. The results of the TEE shall be recorded in the hospital subject files and dedicated eCRF. Hospital Discharge

The hospital discharge data shall be collected and entered in the eCRF before the subject is discharged. The following data listed below shall be collected at hospital discharge or within 30 days of implant:

- Subject status
- Physical evaluation (including cardiac rhythm and NYHA functional classification)
- Medications
- Hemodynamic data or echocardiographic examination measured at investigational site (MPG; PPG, EOA, aortic regurgitation with severity and location)
- SAEs
- Transthoracic echocardiogram (TTE)

7.5. ANTICOAGULATION / DUAL ANTIPLATELET DISCONTINUATION (OR PLANNING) VISIT

This visit may be done by the subject's primary care physician as part of the standard of care for the subject. If done at a location other than the research location, the documentation of the visit will need to be obtained, reviewed by the site PI, and filed in the subject's research records. The visit details may then be entered in the EDC

system and made available for monitoring/source data review. Any part of the evaluation not completed will be considered a protocol deviation.

For subjects discharged with anticoagulation or dual antiplatelet therapy, (see Appendix 4 for American College of Cardiology guidelines for anticoagulation therapy¹¹) an additional visit shall be performed to assess the possibility to stop the anticoagulation or antiplatelet therapy and plan the CT scan. The discontinuation of anticoagulation or antiplatelet therapy is usually around 3 months after surgery in subjects without a further clinical need for this treatment. This additional visit shall evaluate the following information:

- Subject status
- Physical evaluation (including cardiac rhythm and NYHA functional classification)
- Medications
- SAEs

Subjects which are not able to come off ACT/DAPT treatment will remain in the study and followed through the 1-year evaluation.

7.6. 1ST CT SCAN VISIT (1 TO 6 MONTHS FOLLOW-UP VISIT)

This visit is intended to be done a minimum of 30-days after the initial discontinuation of anti-coagulation or dual antiplatelet therapy; usually between 1-6 months postimplant, or at least one month after discharge for subjects discharged without anti-coagulation therapy. Follow-up evaluations are to be conducted in an office, hospital or clinic setting and are to be performed by the PI or his/her designee.

The following data listed below shall be collected:

- Subject status
- Physical evaluation (including cardiac rhythm and NYHA functional classification)
- Medications
- Hemodynamic data from TTE examination measured at investigational site (MPG; PPG, EOA, aortic regurgitation with severity and location)
- CT Scan

- TEE only in subjects that are unable to undergo CT scan at the time of followup
- Medications
- SAEs

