1. SYNOPSIS

Clinical Investigation Plan date	05 / DEC / 2018			
Revision number	В			
	BE havior of valve L eaflets and the I ncidence of r E duced mobility post-surgical aortic val VE implant (BELIEVE)			
Title of study				
	Clinical investigation of leaflet motion in commercially approved LivaNova Perceval bioprosthetic aortic heart valve			
Coordinating Investigators	[name].			
Coordinating Investigators	[name].			
	Enrollment phase: approximately 24 months (2 years)			
Study duration	Follow up phase: 1 year			
	Total duration time: approximately 3 years			
Planned study period	The study started in Q4-2017, after the regulatory and ethical requirements of the regulations/guidelines were completed. Planned completion is Q1-2020 after the 1-year follow-up of the last subject.			
Number of study centers planned	Approximately 11 sites			
Study type	Single-arm, interventional study			
Study design	Prospective, multi-center study			
Primary objective:	The purpose of this study is to report on the overall incidence of reduced leaflet motion identified by CT imaging in the LivaNova Perceval bioprosthetic aortic heart valve up to 1 year post- implant in subjects that are off anticoagulation/dual antiplatelet therapy (ACT/DAPT) for at least 30 days.			
Secondary objectives:	The main secondary objective is to assess all relevant device and subject demographics, procedural events through hospital discharge and short-term outcomes, as described in the secondary endpoints section.			

Primary endpoint	The primary endpoint is the incidence of reduced leaflet motion measured by 4D volume-rendered CT-imaging, as assessed by an independent Core Laboratory (Core Lab) at minimum 1 month after the end of anticoagulation (ACT) or dual antiplatelet therapy (DAPT) (expected within 1 to 6 months postimplant, preferably 3 months).				

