3.1. PRIMARY OBJECTIVES

The purpose of this study is to report the overall incidence of reduced leaflet motion identified by CT imaging in the LivaNova Perceval bioprosthetic aortic heart valve up to 1 year post implant in subjects that are off anticoagulation for at least 30 days.

The primary objectives will be assessed using primary endpoint described in Section 6.3.6.

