2 STUDY DESIGN

2.1 STUDY OBJECTIVES

2.1.1 Primary objective

The purpose of this study is to report the overall incidence of reduced leaflet motion identified by four-dimensional (4D), volume-rendered, computed tomography (CT) imaging in LivaNova Perceval bioprosthetic aortic heart valve up to 1 year post-implant on subjects that are off anticoagulation for at least 30 days.

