10 PRIMARY ANALYSIS

10.1 Primary endpoint

The primary endpoint for the study is the incidence of reduced leaflet motion at a minimum of 30 days after the date of hospital discharge or ACT/DAPT discontinuation recorded on "Visit" e-CRF (expected within 1 to 6 months post-implant, preferably 3 months), as assessed by an independent Core Lab.

The valve leaflets will be assessed using 4D volume-rendered CT imaging or TEE for subjects unable to undergo CT scan (e.g. inappropriate renal function). Leaflet motion in all leaflets will be defined as normal, mildly reduced (<50% reduction in leaflet opening), moderately reduced (50-70% reduction in leaflet motion), severely reduced (>70% reduction in leaflet motion) and immobile (no or negligible leaflet motion).

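### The objective is incidence in subjects off ACT/DAPT for at least 30 days, but the primary analysis never checks therapy status at the first CT

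*Protocol*

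**What the plan says.** **Objective.** The protocol synopsis restricts the target to "subjects that are off anticoagulation/dual antiplatelet therapy (ACT/DAPT) for at least 30 days". Protocol 3.1 and SAP 2.1.1 name anticoagulation only ("in subjects that are off anticoagulation for at least 30 days"; "on subjects that are off anticoagulation for at least 30 days"). All three describe what is true of the subject, not how long ago something happened.

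**Timing of the first CT.** There are three wordings:
- Protocol 7.6: "This visit is intended to be done a minimum of 30-days after the initial discontinuation of anti-coagulation or dual antiplatelet therapy", "or at least one month after discharge for subjects discharged without anti-coagulation therapy".
- Protocol 6.3.6: "at minimum 1 month after the end of the anticoagulation or dual antiplatelet therapy". Subjects discharged without such therapy are timed from discharge.
- SAP 10.1: "at a minimum of 30 days after the date of hospital discharge or ACT/DAPT discontinuation recorded on" the visit form.

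**Analysis.** SAP 10.3 assigns the primary outcome from the first CT in all SAF subjects. SAP 10.4 divides by a population at risk within the SAF and does not define it by therapy status. Protocol 7.5 keeps subjects who cannot stop ACT/DAPT in the study, and the schedule of procedures lists the first CT for all subjects.

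**Data.** Medications are recorded at the CT visit (protocol 7.6), and the use of these drugs is assessed at each follow-up visit (protocol 7.11). The derivations in SAP 18.13 use the discontinuation date and the discharged-on-therapy indicator. They contain no variable for a restart or a first start.

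**The concern.** A state and an elapsed time agree only if nothing changes after the date. They disagree for a subject who stops and then restarts before the scan, and for a subject discharged off therapy who starts it afterwards. Both can meet a rule counted from the first stop or from discharge while on treatment at the CT. A subject who never stops has no discontinuation date, but if scanned is not kept out of the SAF analysis.

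What is at stake is which population the headline figure describes. Followed as written, the plan estimates incidence in scanned SAF subjects whatever their therapy at the scan, while the objective names subjects off therapy. Protocol 2.1 reports a lower rate of reduced motion on therapeutic anticoagulation than on subtherapeutic or none, so the two populations may differ on the outcome. The exact interval does not reflect such a difference.

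**Working it through.** **1. Does any provision restore the off-therapy condition?**

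| Provision | What it uses | Corrects the primary estimate? |
|---|---|---|
| SAP 10.3, 10.4 | First-CT result, all SAF | No therapy condition |
| SAP 5.3 ACT/DAPT subgroup | Status at discharge or 30 days after implant | No; not status at the scan |
| SAP 8.3 | ACT/DAPT status and changes, tabulated over visits | No; descriptive only |
| SAP 11.2 | Drugs used and stopped at least 30 days before the first CT | No; secondary, and silent on restarts |
| SAP 11.5, time free from ACT/DAPT | Stop date to first leaflet evaluation | No; not interrupted by a restart |
| SAP 6.4, 10.5 per-protocol set | Major endpoint-related deviations | Not determinable; sensitivity analysis only, and the list is in a document not supplied |

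**2. The plan's own precision figure.** Inputs from protocol 10.2 are 75 scans, an exact two-sided 90% interval, width below 13% when the proportion is below 10%, and 15% attrition. Clopper-Pearson limits for x events in n are the 5% quantile of Beta(x, n−x+1) and the 95% quantile of Beta(x+1, n−x).
- 7/75 = 9.3%: 4.5% to 16.8%, width 12.35%.
- Exactly 10% (x = 7.5, by interpolation): 4.9% to 17.6%, width 12.7%.
- Enrolment: 75/0.85 = 88.2; the plan states about 88.

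The stated figures reproduce.

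**3. Effect on the reported incidence.** Let p be the off-therapy incidence, f the share of scans taken on therapy, and r the on-therapy incidence relative to off-therapy. Then

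reported = p × (1 − f + f × r).

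The documents give neither f nor r. I assume f = 2% to 15% and r = 0, 0.5 or 1. I take p = 10%, which lies within the 8–12% quoted for surgical valves in protocol 2.1.

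| f | r = 0 | r = 0.5 | r = 1 |
|---|---|---|---|
| 2% | 0.10 × 0.98 = 9.8% | 0.10 × 0.99 = 9.9% | 10% |
| 10% | 0.10 × 0.90 = 9.0% | 0.10 × 0.95 = 9.5% | 10% |
| 15% | 0.10 × 0.85 = 8.5% | 0.10 × 0.925 = 9.3% | 10% |

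The largest shift is 1.5 points, or 0.015 × 75 = 1.1 events.

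**4. Precision if only off-therapy scans count.** Off-therapy scans = 75 × (1 − f). The width is taken at a 10% proportion. Enrolment to keep 75 off-therapy scans = 75/(0.85 × (1 − f)).

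| f | Off-therapy scans | 90% CI width | Enrolment for 75 |
|---|---|---|---|
| 0 | 75 | 12.7% | 88.2 |
| 2% | 73.5 | 12.8% | 90.0 |
| 5% | 71.25 | 13.05% | 92.9 |
| 10% | 67.5 | 13.4% | 98.0 |
| 15% | 63.75 | 13.9% | 103.8 |

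At a 10% proportion the width stays below 13% down to 72 scans.

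**The case against.** The strongest reply is that this is mostly a wording matter. The word *initial* stands only in protocol 7.6, a visit-scheduling paragraph. The endpoint definition in 6.3.6 speaks of the end of therapy, which arguably excludes someone who has restarted, and SAP 10.1 says only discontinuation. Subjects with a condition requiring long-term ACT/DAPT are excluded at entry. The schedule of procedures gives the first CT a 60-day window after the 30-day minimum, which limits the time for restarts, although the visit window guide in 7.10 allows 60 to 240 days after discontinuation. Follow-up therapy status will be tabulated, the per-protocol analysis may remove some of these scans, and the study is descriptive.

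Much of this stands as to size, and a reader should not infer that SAP 10.1 itself counts from the first stop. It does not answer the main point: no provision applies a therapy condition to the primary numerator or denominator. The discharge-date route also stays open under every wording.

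Two further readings are tempting and unsupported. One is that such subjects necessarily dilute the incidence. The background comparison concerns therapeutic anticoagulation and says nothing about DAPT, and a restart prompted by symptoms could select subjects at higher risk. The other is to read the 11 of 21 in protocol 2.1 as a recovery rate under anticoagulation. The sentence leaves open whether 11 counts those treated or those who recovered, and the recovery it reports was full or partial.

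**Conclusion.** The concern holds as a mismatch between the objective and the analysed population. Following the plan exactly gives an incidence that can include subjects on restarted, newly started or never-stopped therapy at the scan.

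The size is unknown and may be small. Under the assumed shares of 2% to 15%, a 10% incidence would be reported as 9.8% to 8.5% at the extreme of no on-therapy cases, against an interval about 12.7 points wide. There is no shift if on-therapy risk is equal. The downward direction is supported only for therapeutic anticoagulation.

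The sample-size statement is arithmetically sound; a reader should not conclude that it is wrong. It simply does not guarantee that the 75 evaluable scans are off-therapy scans. The change is worth making because it aligns the estimate with the objective using data already collected.

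**What to change.** - In SAP 10.3, 10.4 and 18.13, define the population at risk with a flag: no ACT or DAPT record active on any of the 30 days before the first-CT date, derived from the medication data.
- Report the primary incidence in flagged subjects. Report separately the incidence in subjects on therapy within 30 days of the scan, and in all scanned SAF subjects.
- Restate the expected interval width for the number of off-therapy scans. Protocol 4.4 already allows continued enrolment to reach 75 evaluable scans; say whether that target means off-therapy scans.
- Reconcile protocol 6.3.6, protocol 7.6 and SAP 10.1 with the objective, and the synopsis objective (ACT/DAPT) with protocol 3.1 and SAP 2.1.1 (anticoagulation only). Which scan-timing rule applies is for the sponsor to decide.

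The cost is SAP wording, one derived flag and a few scans leaving the primary denominator. At a 10% proportion, losing 5% of scans takes the width from 12.7% to about 13.05%, just over the stated 13%, and losing 10% takes it to 13.4%. Holding 75 off-therapy scans would then need about 93 or 98 enrolled instead of about 88.

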7.7. UNSCHEDULED VISITS

Unscheduled visits in symptomatic subjects (subjects with symptoms of reduced leaflet function) and any other subjects needing a study related follow-up visit that is not covered by the standard visit schedule. The following items may be captured:

- Subject status
- Physical evaluation (including cardiac rhythm and NYHA functional classification)
- Medications
- Transthoracic echocardiogram (TTE) (if available)
- SAEs

7.8. 2ND CT SCAN VISIT/REDUCED LEAFLET VISIT (AFTER THE 1ST CT SCAN, BUT PRIOR TO 1-YEAR FOLLOW-UP VISIT)

This visit is intended provide a 2nd follow-up 4D CT scan if the 1st CT scan showed reduced leaflet motion. This second CT scan visit is expected at approximately 6-10 months, but prior to 1 year follow-up. This follow-up evaluation shall be conducted in an office, hospital or clinic setting by the PI or his/her designee, at a time designated by the PI.

If the 1st CT scan showed no signs of reduced leaflet motion, a repeat 4D CT is not mandated and will only be done if it becomes clinically indicated. For subjects unable to undergo a contrast CT scan (e.g. inadequate renal function), a TEE may be performed.

The following data listed below shall be collected if this visit is required:

- Subject status
- Physical evaluation (including cardiac rhythm and NYHA functional classification)
- Medications

- Hemodynamic data from TTE examination measured at investigational site (MPG; PPG, EOA, aortic regurgitation with severity and location)
- CT scan with contrast
- TEE only in subjects that are unable to undergo CT scan at the time of follow-up
- Medications
- SAEs

7.9. 1-YEAR FOLLOW-UP VISIT

This visit is intended as a clinic visit at 1 year \pm 1 month after the day of the surgery. Follow-up evaluations shall be conducted in an office, hospital or clinic setting and are to be performed by the PI or his/her designee. **All efforts should be made to ensure that the subject comes to the clinic.**

The following data listed below shall be collected:

- Subject status
- Physical evaluation (including cardiac rhythm and NYHA functional classification)
- Medications
- Hemodynamic data from TTE examination measured at investigational site (MPG; PPG, EOA, aortic regurgitation with severity and location)
- Medications
- SAEs

The information collected during these follow-up evaluations, including serious adverse events, will be recorded on eCRFs in the electronic data capture (EDC) system according to the schedule of procedures (Table 4)

